8.2 Complication

The numbers and percentages of subjects are presented for all complications and by primary SOC and PT.

8.3 Concomitant Medications for Target Disease (Itching)

For concomitant medications used for the treatment of the target disease (itching) from the start of the study treatment to the end of the treatment period, the numbers and percentages of subjects will be presented by generic name and route of administration.

8.4 Concomitant Medications for Complications

For the concomitant medications used for complications from the start of the study treatment to the end of the treatment period, the numbers and percentages of subjects will be presented by generic name and route of administration.

9. Treatment compliance

9.1 Number of Doses

For the number of doses of the study drug, the numbers and percentages of subjects who fall under the following categories will be presented.

Category: $1 \le 3$, $4 \le 6$, $7 \le 9$, $10 \le 12$, $13 \le 15$, $16 \le 18$, $19 \le 21$, $22 \le 24$, $25 \le (unit: times)$

9.2 Treatment Compliance

Summary statistics will be presented.

9.3 Treatment Duration

Summary statistics will be presented.

9.4 Average Administration Liquid Volume

The average administration liquid volume will be obtained by dividing the total administration liquid volume of the study drug in the treatment period by the number of doses. Summary statistics will be presented.

9.5 Change Status of Administration Liquid Volume

For changes from the initial administration liquid volume throughout the treatment period, the

Statistical Analysis Plan	Protocol No. MR13A9-4
	Version: 1.0

numbers and percentages of subjects who fall under the following categories will be presented.

Category:

- No change: Subjects who received only the initial administration liquid volume throughout the treatment period
- Dose increase: Subjects who received an administration liquid volume larger than the initial administration liquid volume (excluding the cases with a dose increase and decrease)
- Dose decrease: Subjects who received an administration liquid volume smaller than the initial administration liquid volume (excluding the cases with a dose increase and decrease)
- Dose increase and decrease: Subjects who received administration liquid volumes larger and smaller than the initial administration liquid volume

9.6 Average Dose per Dry Weight

The total dose of the study drug per dry weight during the treatment period is divided by the number of doses to obtain the average dose per dry weight.

Summary statistics will be presented.

10. Efficacy

10.1 Primary Endpoint

The primary endpoint is the NRS score. The assessment time points and their evaluated time windows in the screening and treatment periods, and follow-up period are shown in Table 10.1-1 and Table 10.1-2, respectively.

Table 10.1-1 Assessment Time Points and Evaluated Time Windows in the Screening and Treatment Periods

Time point	Evaluated time window ^{a)}
Week -1	From Day -13 to Day -7
Week 0 (baseline)	From Day –6 to Day 1
Week 1	From Day 2 to Day 8
Week 2	From Day 9 to Day 15
Week 3	From Day 16 to Day 22
Week 4	From Day 23 to Day 29
Week 5	From Day 30 to Day 36
Week 6	From Day 37 to Day 43
Week 7	From Day 44 to Day 50
Week 8	From Day 51 to Day 57

a) The start date of the treatment period will be regarded as Day 1 and the previous day of the start date of the treatment period will be regarded as Day -1.

Statistical Analysis Plan Protocol No. MR13A9-4 Version: 1.0

Table 10.1-2 Assessment Time Points and Evaluated Time Windows in the Follow-up Period

Time point	Evaluated time window ^{a)}
Follow-up Week 1	From Day 1 to Day 7
Follow-up Week 2	From Day 8 to Day 14

a) The start date of the follow-up period (the date of treatment period completion or the next day of the date of discontinuation) will be regarded as Day 1.

The mean NRS score at each time point will be calculated as follows.

Mean NRS score at each time point = Sum of the NRS score observed during the evaluated time window ÷ Number of days when NRS score was observed during the evaluated time window

The change from baseline in the mean NRS score at each time point will be calculated as follows:

Change from baseline in the mean NRS score at each time point = Mean NRS score at each time point - Mean NRS score at baseline

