9.4 Efficacy Endpoints

9.4.1 Symptom diary (electronic diary)

The principal investigator, subinvestigator, or clinical research coordinator will instruct each subject how to record the symptom diary, as well as register the information on each subject in the electronic diary system to prepare for the start of recording. The subject will record the following information 1) and 2) in the symptom diary from the next day of the start date of the screening period until the end date of the follow-up period.

1) NRS score

Looking back on the period between the time of awakening on the previous day of assessment and the time of awakening on the day of assessment (including sleeping hours) once daily, subjects will assess the NRS score for the most severe itching by themselves and record the score in the symptom diary. According to Appendix 3, the most severe itching within the day will be assessed in integer on a scale ranging from 0 to 10, where 0 represents no itching and 10 represents worst itching imaginable.

2) Shiratori's severity criteria

Looking back on the period between the time of awakening on the previous day of assessment and the time of awakening on the day of assessment (including sleeping hours) once daily, subjects will assess the degree of itching by themselves and record the score in the symptom diary. According to Appendix 4, the symptoms during the day and the night will be assessed on a scale ranging from 0 to 4, where 0 represents no symptoms and 4 represents severe itching.

- Degree of the symptom during the day: Degree of the most severe itching during the day between the time of awakening on the previous day of assessment and the time of going to bed on the previous day of assessment
- Degree of the symptom during the night: Degree of the most severe itching during the night between the time of going to bed on the previous day and the time of awakening on the day of assessment

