Day of the week	_	Mon /Tue	Mon /Tue	Mon /Tue	Wed /Thu	Fri /Sat	Mon /Tue	Wed /Thu	Fri /Sat	Mon /Tue	Wed /Thu	Fri /Sat	Mon /Tue	/Thu	Fri /Sat	Mon /Tue	Wed /Thu	Fri /Sat	Mon /Tue	Wed /Thu	Fri /Sat	Mon /Tue	Wed /Thu	Fri /Sat	Mon /Tue	/Thu	Fri /Sat	Mon /Tue	Wed /Thu	Fri /Sat	Mon /Tue
Informed consent ^{b)}	•																														
Eligibility assessment	•	•		•																											
Subject demographics	•	•																													
Subject registration	Primary	Seconda ry		Tertiary																											
Study treatment				•	•	•	•	•	•	•	•	•	•	•	•	•	•	•	•	•	•	•	•	•							
NRSc)																															
Shiratori's severity criteria ^{c)}																													_		\longrightarrow
Adverse events																															
Concomitant medications/therapies																													—	—	₩
Specific signs/symptoms ^{d)}			•	-			•			•			•			•			•			•			١.			•	+		•
Prohibited concomitant			•	_			•			•			•			•			_			_			Ť			Ť	┼	├ ─	Ť
medications																															
Hemodialysis conditions																													$\overline{}$	$\overline{}$	\rightarrow
Skindex-16 5-D itch scale				•												•									•						
PGIC																									•				 		+
Body weight ^{e)} 12-lead ECG ^{e)}		•		•																					•						
Vital signs ^{e)} Laboratory tests ^{e)}		•		•			•			•						•									•						•
Postdialysis BUN Postdialysis weight		•																													
Dependency assessmentf)																									•			•			
Serum pregnancy testg)		•																							•						
Pharmacokineticsh)							•	•		•						•	•					•	•		•						

- a) Assessments and tests will be performed on the day of the first dialysis of each week, unless prescribed otherwise.
- b) Consent for study participation must be obtained prior to the start of the screening period.
- c) To be recorded in the symptom diary once daily from the next day of the start date of the screening period until the visit day at Week 10.
- d) Subjects will be examined for specific signs/symptoms every week (Monday or Tuesday) from Week -1 until Week 10.
- e) To be performed before dialysis.
- f) To be performed before dialysis at Week 8.
- To be performed only in women of childbearing potential (within 1 year of their last menstrual period and who have not undergone total hysterectomy or bilateral total ovariectomy).

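### For completers, the footnote starting Follow-up Day 1 on the undefined completion date conflicts with protocol 7.2.3; with completion on Day 57, that score counts in both Week 8 and Follow-up Week 1

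*SAP*

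**What the plan says.** - **Treatment-period windows (SAP Table 10.1-1, protocol Table 13.5.1-1).** "The start date of the treatment period will be regarded as Day 1", and the Week 8 window runs "From Day 51 to Day 57".
- **Follow-up windows (SAP Table 10.1-2, protocol Table 13.5.1-2).** Follow-up Week 1 runs "From Day 1 to Day 7" and Follow-up Week 2 "From Day 8 to Day 14", on a separate day count. Footnote a) starts that count on "the date of treatment period completion or the next day of the date of discontinuation". Completers thus start on the date itself, and discontinued subjects on the following day.
- **Definition of follow-up (protocol 7.2.3).** Follow-up is the two weeks that come after the treatment period has ended, or after the discontinuation assessments.
- **Visits (protocol 10.12 and 10.13).** Week 9 is labelled the first follow-up week and Week 10 the second.
- **Diary.** The recall period of each NRS entry is set in protocol 9.4.1, whose instruction opens: "Looking back on the period between the time of awakening on the previous day of assessment and the time of awakening on the day of". Each entry thus spans one awakening to the next. Study Schedule footnote c) has the diary kept daily "from the next day of the start date of the screening period until the visit day at Week 10".
- **Use.** SAP 10.1.2.1 to 10.1.2.3, 10.2.1.1 and 10.2.1.2 report Follow-up Weeks 1 and 2. SAP 6.5.1 treats every time point other than Week 8 as a reference.

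Neither document defines the date of treatment period completion or says which window takes a shared day.

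**The concern.** Each window in SAP Table 10.1-1 ends on a weekly visit, and the visit-day score belongs to the week just ended. Day 1, for example, closes Week 0, and Week 1 opens on Day 2. The follow-up footnote breaks this pattern for completers: the day that closes the last treatment window also opens the first follow-up window. It also gives completers and discontinued subjects different starting rules.

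The follow-up windows show what happens to itch once MR13A9 stops, and NRS and the Shiratori score are the only efficacy measures still collected then. An end-of-treatment score inside an off-treatment mean would tend to hide part of any return of itch. What is at stake is how those descriptive follow-up results read, not the trial's main conclusion.

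**Working it through.** **1. Reproduce the plan's windows.** With the first dose on Day 1 and visits on the same weekday, the Week k visit falls on Day 7k + 1, and the seven days ending there are Days 7k - 5 to 7k + 1.
- k = 1: Days 2 to 8.
- k = 8: 56 - 5 = 51 to 56 + 1 = 57.

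This matches the table for Weeks 1 to 8. Week 0 (Day -6 to Day 1, with no Day 0) is also seven days ending on the visit. By the same rule, the Week 9 visit is Day 64 and the Week 10 visit, the last diary day, is Day 71.

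**2. Place the follow-up windows on the same axis.** Completion is taken as the Week 8 visit, Day 57.

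| Follow-up Day 1 for completers | Follow-up Week 1 | Follow-up Week 2 | Shared with Week 8 | In no window |
|---|---|---|---|---|
| Completion date (footnote as written) | Days 57-63 | Days 64-70 | Day 57 | Day 71 |
| Day after completion | Days 58-64 | Days 65-71 | none | none |

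The next-day start ends each window on its labelled visit (Days 64 and 71). The footnote as written also moves the Week 9 visit-day score (Day 64) into Follow-up Week 2.

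**3. What the Day 57 score measures.** Under protocol 9.4.1 it covers awakening on Day 56 to awakening on Day 57, so it closes before the Week 8 dialysis session. It is the same kind of entry as the Day 8 or Day 15 score, which the plan assigns to the week just ended.

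**4. Size.** Let d(t) be the active-minus-placebo difference in NRS on Day t. With a full diary:
- as written: [d(57) + ... + d(63)] / 7
- aligned to visits: [d(58) + ... + d(64)] / 7
- shift caused by the footnote: [d(57) - d(64)] / 7

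One score in seven (1/7 = 14%) is an end-of-treatment score. Protocol 7.6.2 plans Week 8 differences of -0.6, -1.3 and -1.3 for 0.25, 0.5 and 1.0 μg/kg. Suppose the whole planned difference is present on Day 57 and none is left by Day 64:
- 0.5 and 1.0 μg/kg: -1.3 / 7 = -0.19
- 0.25 μg/kg: -0.6 / 7 = -0.09

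Any effect remaining on Day 64 makes the shift smaller. For a subject with only the four diary days that SAP 6.2 requires, Day 57 could weigh 1/4 rather than 1/7.

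**5. What is not affected.** The Week 8 window stays at Days 51-57, and the primary model uses Weeks 1 to 8 only (SAP 10.1.1.1.1).

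**The case against.** **It may be a wording slip.** Both documents are translations, and the source may have applied the next day to completion as well as to discontinuation. Protocol 7.2.3 and the visit labels fit that reading exactly. This is plausible but cannot be checked from these documents. The same wording stands in both and, programmed literally, gives overlapping windows, so clarification is still needed.

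**Day 57 is inferred.** This stands. It rests on the Week 8 visit and the Week 8 window both belonging to the treatment period, and on visits keeping to schedule. A reader might count eight full weeks and infer completion on Day 56, with two shared days and a carry-over of 2 × 1.3 / 7 = -0.37. Neither document names Day 56 as the completion date, so that figure is not supported.

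**The size calculation is extreme.** This also stands. The Study Schedule shows no dose at Week 8; the last scheduled dose is the Friday or Saturday of Week 7 (Day 50 + 4 = Day 54). If the effect ended at once, Day 57 would already carry little of it. If it fades slowly, later follow-up days carry real residual effect too; protocol 1.3.2.1 reports a half-life of 40.0 to 49.3 hours after the third dose. Either way the shift is below the bound.

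**The outputs are secondary.** This stands as well. Follow-up NRS and Shiratori results are summaries and unadjusted tests, and the study objectives do not mention durability. Six of the seven days in Follow-up Week 1 are unaffected, and Follow-up Week 2 contains no treatment-period score. Losing Day 71 leaves that window seven days long.

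**Conclusion.** The inconsistency is real and its severity is minor. The footnote in both documents conflicts with protocol 7.2.3 and with the next-day start for discontinued subjects. For an on-schedule completer, with completion taken as Day 57, it counts Day 57 twice, shifts Day 64 into Follow-up Week 2 and leaves Day 71 unused.

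With full diaries, the carried-over difference in Follow-up Week 1 is at most about -0.19 for 0.5 and 1.0 μg/kg and about -0.09 for 0.25 μg/kg. These bounds assume that the Day 57 difference is no larger than planned and that none remains by Day 64; the true shift is probably smaller. The outputs concerned are NRS change, mean and responder rates, and the Shiratori scores, all in follow-up only.

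A reader might infer that the primary result is contaminated, or that persistence of effect in the active groups is materially overstated. The documents support neither: the Week 8 window and model do not change, and no effect on responder rates or Shiratori scores has been shown.

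**What to change.** In footnote a) of SAP Table 10.1-2 and of protocol Table 13.5.1-2, define the date of treatment period completion as the Week 8 visit and set Follow-up Day 1 for completers to the next day. Follow-up Week 1 is then Days 58-64 and Follow-up Week 2 is Days 65-71 for an on-schedule subject, and each diary entry from the Week 8 window onward is used once.

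While the footnote is open, reconcile its discontinuation clause with protocol 4.3.2. The footnote counts from the date of discontinuation; 4.3.2 counts from the discontinuation assessments, which may fall on a later dialysis day.

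The cost is one footnote in each document and one line of programming. No new data are needed and the primary analysis is not altered.

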10.1.1 Primary variable

Change from baseline in the mean NRS score at Week 8 of the treatment period

10.1.1.1 Analysis of the primary variable

10.1.1.1.1 Primary analysis

The primary analysis will be performed using a mixed-effects model for repeated measures (MMRM) with the change from baseline in the mean NRS score at each time point as an objective variable; treatment group, time point, and treatment group-by-time point interaction as fixed effects; baseline mean NRS score and dynamic allocation factors, including the presence of prior treatment with nalfurafine hydrochloride, and the presence of specific signs or symptoms to be confirmed in the screening period, as covariates; and subject as a random effect.

The analysis will include all available data obtained at each time point between Week 1 and Week 8 of the treatment period. Estimation will be performed using a restricted maximum likelihood method. An unstructured covariance structure will be used to estimate error variance. If the unstructured covariance structure fails to provide convergence, the structure that minimizes Akaike's Information Criterion (AIC), among the Toeplitz, first-order autoregressive, and compound symmetry structures will be used. The degree of freedom will be adjusted with the Kenward-Roger method.

For the primary variable and the change from baseline in the mean NRS score at Week 2 of the treatment period, contrasts will be used to determine the dose-response relationship for the placebo group and the MR13A9 0.25, 0.5, and 1.0 μ g/kg groups. Contrast patterns (placebo, 0.25, 0.5, 1.0 μ g/kg) to be used will include (3, 1, -1, -3), (2, 2, -1, -3), (1, 1, 1, -1, -1), (3, -1, -1, -1), and (3, 1, -2, -2).

The number of subjects, adjusted mean of the change, standard error, and two-sided 95% confidence interval in each group at each time point will be presented, and the adjusted mean and standard error will be presented in graphs. The adjusted mean between-group difference in the change at each time point for the placebo group and the MR13A9 0.25, 0.5, and $1.0~\mu g/kg$ groups and its two-sided 95% confidence interval as well as the p-value will be

Protocol No. MR13A9-4
Version: 1.0

presented. P-values will be presented for each contrast pattern used to examine the dose-response relationship.

Assessment time points: Weeks 1, 2, 3, 4, 5, 6, 7, and 8

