7.6.2 Rationale for the sample size

In the non-Japanese phase II clinical study (CR845-CLIN2101), the change from baseline in NRS score at Week 8 (mean \pm standard deviation) was -3.9 ± 2.48 , -2.8 ± 2.24 , and -3.4 ± 2.34 in the MR13A9 0.5 μ g/kg, 1.0 μ g/kg, and combined (CR845 all doses) groups, respectively, versus -1.9 ± 2.29 in the placebo group. The difference in the change from

baseline in NRS score (least squares mean \pm standard error) in each of the MR13A9 0.5 μ g/kg, 1.0 μ g/kg, and combined groups versus the placebo group was -1.8 ± 0.50 , -0.8 ± 0.52 , and -1.3 ± 0.41 , respectively.

For the present study, the MR13A9 0.5 and 1.0 μ g/kg groups were assumed to have a similar change in NRS score at Week 8 of the treatment period to that observed in the MR13A9 combined group in the non-Japanese phase II clinical study. The MR13A9 0.25 μ g/kg group, for which no efficacy results were obtained, was assumed to have about half the change in NRS score assumed above. The mean difference in NRS score between each of the MR13A9 0.25, 0.5, and 1.0 μ g/kg groups and the placebo group was assumed to be -0.6, -1.3, and -1.3, respectively, with a common standard deviation of 2.5. When the dose-response relationship for the MR13A9 0.25, 0.5, and 1.0 μ g/kg groups was evaluated using the contrast patterns shown in "13.5.2.1.1 Primary analysis," with a two-sided significance level of 5% and a sample size of 60 subjects per group, a contrast pattern of 3, 1, -2, -2 (placebo, 0.25, 0.5, 1.0 μ g/kg) produced a statistical power of 91.7%. Statistical power is more than 80% when the MR13A9 0.5 or 1.0 μ g/kg group (60 subjects per groups) was compared with the placebo group.

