With respect to the mean difference in NRS score at Week 2 of the treatment period, the MR13A9 0.5 and 1.0 μ g/kg groups were assumed to show a difference considered clinically meaningful versus the placebo group, and the MR13A9 0.25 μ g/kg group was assumed to show about half the difference above. The mean difference in NRS score versus the placebo group was assumed to be -0.4, -0.8, and -0.8 in the MR13A9 0.25, 0.5, and 1.0 μ g/kg groups, respectively, with a common standard deviation of 1.9. As with the evaluation of the doseresponse relationship at Week 8 of the treatment period, when the dose-response relationship for the MR13A9 0.25, 0.5, and 1.0 μ g/kg groups was evaluated using the contrast patterns, with a two-sided significance level of 5% and a sample size of 60 subjects per group, a contrast pattern of 3, 1, -2, -2 (placebo, 0.25, 0.5, 1.0 μ g/kg) produced a statistical power of 76.4%.

8. Subject Instructions and Management

The principal investigator or subinvestigator should sufficiently explain the significance and objectives of the study to subjects, and instruct and manage them especially for the following:

- 1) Confirm the absence of somnolence, dizziness, or similar symptoms after receiving the study drug and return home. Report any symptoms to the principal investigator or subinvestigator. Pay attention during hazardous machine operation and automobile driving during the treatment period. Avoid hazardous machine operation and automobile driving on the day of study treatment.
- 2) Maintain the symptom diary in subject every day. Record symptoms in the designated form and bring it at visit dates if any electronic diary system trouble makes the maintenance of the symptom diary impossible.
- 3) Take all prescribed drugs other than the study drug properly as instructed.
- 4) Be sure to visit the study site as scheduled. Inform the study site in advance if it is impossible to visit for some unavoidable reason. Visit the study site at the same time at every visit whenever possible.
- 5) Report the drug(s) used currently to the principal investigator or subinvestigator before participation in the study. Consult the principal investigator or subinvestigator before use about any new drug prescribed at other medical departments or hospitals or any over-the-

counter drug to be started. Report to the principal investigator or subinvestigator immediately if it was inevitable to use any drug without consultation.

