10.1.1.1.2 Sensitivity analysis

The sensitivity analyses shown below will be performed to determine the robustness of the analysis results. In the individual sensitivity analyses, as with the primary analysis, contrasts will be used to determine dose-response relationships and estimate treatment effects. However, this is not presented in graphs.

Multiple imputation (MI) will be performed 100 times.

1) MI - MMRM

Multiple imputed data will be generated in the MI procedures shown below. Each imputation data will be analyzed using the same MMRM model as that for the primary analysis, and the results of the analyses will be combined. Imputation will be performed for all available data obtained at each time point between Week 0 and Week 8 of the treatment period.

- (1) Non-monotone missing data will be imputed with a Markov Chain Monte Carlo (MCMC) method.
- (2) Monotone missing data will be imputed with an imputation formula generated using a regression model developed based on the data from all the groups.

2) Placebo MI - MMRM

Multiple imputed data will be generated in the MI procedures shown below. Each imputation data will be analyzed using the same MMRM model as that for the primary analysis, and the results of the analyses will be combined. Imputation will be performed for all available data obtained at each time point between Week 0 and Week 8 of the treatment period.

- (1) Non-monotone missing data will be imputed with an MCMC method.
- (2) Monotone missing data will be imputed with an imputation formula generated using a regression model developed based on the data from the placebo group.

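### The primary MMRM fits one baseline-NRS slope to all eight weeks; if that slope drifts over time, the Week 8 estimate may lose a little precision that a baseline-by-week term would recover

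*SAP*

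**What the plan says.** SAP 10.1.1.1.1 and Protocol 13.5.2.1.1 give the same model. Its fixed effects are "treatment group, time point, and treatment group-by-time point interaction". The covariates are "baseline mean NRS score and dynamic allocation factors, including the presence of prior treatment with nalfurafine hydrochloride" and the presence of specific signs or symptoms at screening. No covariate-by-time point term is listed. On the error side, "An unstructured covariance structure will be used to estimate error variance". Treatment effects, week means and residual variances are therefore free by week, while the covariate effects are not.

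No other planned model relaxes this. For both multiple-imputation analyses (SAP 10.1.1.1.2), "Each imputation data will be analyzed using the same MMRM model as that for the primary analysis". The Shiratori, Skindex-16 and 5-D analyses (SAP 10.2.1.1, 10.2.2.1, 10.2.3.1) follow the primary model with their own baseline as covariate. The t-tests in SAP 10.1.2.1 do not adjust for baseline at all.

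The sample-size section (Protocol 7.6.2) takes Week 8 differences from placebo that "was assumed to be -0.6, -1.3, and -1.3, respectively", "with a common standard deviation of 2.5". For Week 2 it takes -0.4, -0.8 and -0.8, "with a common standard deviation of 1.9".

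**The concern.** With an unstructured covariance, a single slope is estimated as a generalised least squares average of the eight weekly slopes, and less variable weeks tend to count for more. The plan expects less variability at Week 2 than at Week 8. If change depends more strongly on baseline by Week 8 than it does early on, the common slope is too shallow for Week 8. Some variation due to baseline then stays in the Week 8 residual.

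Week 8 is the primary time point and carries the dose-response contrasts. Any loss of precision there comes from a modelling choice and could be avoided with data already collected.

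**Working it through.** **Inputs from the documents.** Two-sided 5% and 60 per group ("with a two-sided significance level of 5% and a sample size of 60 subjects per group"); Week 8 differences -0.6, -1.3, -1.3; SD 2.5 at Week 8 and 1.9 at Week 2; contrast (3, 1, -2, -2).

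**Inputs assumed, because the documents give none.** Baseline SD 1.3 to 1.6. Slope of change on baseline linear in week, from between -0.1 and -0.2 (Week 1) to between -0.35 and -0.6 (Week 8). SD of change on a straight line through 1.9 and 2.5, so 1.8 at Week 1. Residual correlation AR(1) 0.9, AR(1) 0.8, a mixture 0.3 + 0.7 × 0.85^lag, or compound symmetry (CS) 0.7. Complete data.

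**Step 1: the plan's own figures.** Noncentrality = |Σcμ| / (SD × √(Σc²/n)).
- Week 8: Σcμ = 1×(-0.6) - 2×(-1.3) - 2×(-1.3) = 4.6 and Σc² = 18, so 4.6 / (2.5 × √(18/60)) = 3.359. With 236 df the power is 91.71%, against 91.7% stated.
- Week 2: 2.8 / (1.9 × √(18/60)) = 2.691, power 76.41%, against 76.4% stated.

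These are plain four-group contrasts that take no credit for baseline adjustment.

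**Step 2: weights on the common slope.** With b the vector of weekly slopes and V the residual covariance (including the misfit, solved iteratively), b* = (1'V⁻¹b)/(1'V⁻¹1). With the rising SDs, Weeks 1 to 3 carry roughly 60 to 80% of the weight under the AR and mixed patterns. Under CS 0.7 they carry over 100%, because late weeks mostly get negative weights.

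**Step 3: cost at Week 8.**
- Week-specific slopes: variance = 2.5² - b8² × Var(baseline).
- Common slope: add (b8 - b*)² × Var(baseline).

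Example with baseline SD 1.6, slope -0.1 to -0.6, mixed correlation: b* = -0.230.
- Week-specific: 6.25 - 0.36 × 2.56 = 5.328, SD 2.308.
- Common: 5.328 + 0.370² × 2.56 = 5.679, SD 2.383.
- Ratio 5.679/5.328 = 1.066.

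| Baseline SD | Slope, Week 1 to 8 | Correlation | b* | Variance, week-specific | Variance, common | Increase | Power, week-specific v common |
|---|---|---|---|---|---|---|---|
| 1.5 | -0.3 constant | any | -0.300 | 6.048 | 6.048 | 0 | 92.5% v 92.5% |
| 1.3 | -0.2 to -0.35 | AR 0.8 | -0.250 | 6.043 | 6.060 | 0.3% | 92.54% v 92.47% |
| 1.45 | -0.15 to -0.475 | mixed | -0.223 | 5.776 | 5.909 | 2.3% | 93.6% v 93.1% |
| 1.6 | -0.1 to -0.6 | mixed | -0.230 | 5.328 | 5.679 | 6.6% | 95.2% v 93.9% |
| 1.6 | -0.1 to -0.6 | CS 0.7 | -0.100 | 5.328 | 5.969 | 12.0% | 95.2% v 92.8% |

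The second row and the last two are the ends of the assumed range; the third is its midpoint.

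**Step 4: simulation.** 3,000 trials per scenario under AR(1) 0.9 gave ratios of common-slope to week-specific SE of:
- 1.000 for a constant slope of -0.3;
- 1.004 for -0.2 to -0.4;
- 1.020 for -0.1 to -0.5;
- 1.081 for an extreme -0.1 to -0.7 with baseline SD 2.0.

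The first three used baseline SD 1.5. Mean contrasts were 4.57 to 4.66 against a true 4.6, and the two models differed by no more than 0.004.

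**The case against.** The strongest reply is that the loss is conditional and the condition cannot be checked here. It equals (b8 - b*)² × Var(baseline), and the documents supply neither factor. That the slope steepens over time is an assumption. The early weighting also depends on the covariance: with equal SDs, CS would weight all weeks alike and AR(1) would weight Weeks 1 and 8 alike, and the variance increase over the same assumed slopes falls to 0.2 to 2.2%. The rise in SD rests on two planning values. All of this stands, and it is why the point is worded conditionally.

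The one relevant data source in the protocol suggests little gain from adjustment. In the non-Japanese 8-week study the standard errors of the adjusted differences were 0.50, 0.52 and 0.41 (Protocol 7.6.2). The raw values implied by the SDs and group sizes in Protocol 1.3.2.2 are √(2.48²/44 + 2.29²/45) = 0.51, √(2.24²/41 + 2.29²/45) = 0.49 and, for all doses combined with SD 2.34 and 129 subjects, √(2.34²/129 + 2.29²/45) = 0.40. That study's model and analysed numbers are not described, so this is only suggestive.

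A reader might infer more than the documents support:
- **That the trial is underpowered.** The 91.7% uses SD 2.5 with no adjustment credit. Taking 2.5 as the raw SD of change, the common slope kept at least 91.7% in every scenario tried. If 2.5 is instead the residual SD under the common slope, the stated power still stands and the interaction only adds to it.
- **That the estimate is biased or type I error inflated.** Neither was seen in the complete-data simulations, and randomisation gives no reason to expect it.
- **That missing Week 8 values are mishandled.** Nothing was computed under dropout, so no such claim is made.
- **That Skindex-16 and 5-D lose precision in the same way.** They are modelled at Weeks 4 and 8 only, so the eight-week weighting argument does not carry over, and nothing was computed for them.

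**Conclusion.** The point holds as a minor efficiency matter. As written, one baseline slope applies to all eight weeks and no planned model frees it. If the slope drifts, the Week 8 estimate may lose a little precision. Under the assumed ranges, Week 8 variance rises by about 0.3 to 7% and contrast power falls by about 0.1 to 1.3 points. The figures of 12% and 2.4 points need a CS-like correlation together with the steepest drift and the largest baseline SD. If the slope is constant the loss is zero. What would be forgone is part of a gain that the sample-size calculation never claimed. Severity: nice to have.

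**What to change.** Add the baseline mean NRS-by-time point interaction to the primary MMRM in SAP 10.1.1.1.1, prespecified before unblinding. The imputation analyses inherit it because they reuse the model. For consistency, add the matching baseline-by-time point term to the Shiratori model in SAP 10.2.1.1. For Skindex-16 and 5-D the term would be one extra parameter each and is optional.

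The cost is 7 extra parameters with 240 planned subjects and no new data. With a constant slope, calculated power is the same (92.5% either way) and the simulated standard errors are practically identical. If the sponsor prefers to leave the primary model as it stands, the interaction model could be prespecified as a sensitivity analysis.
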